10.1.2. Reporting Procedure

All events (serious and non-serious) must be reported with Investigator's assessment of the event's seriousness, severity, and causality to the (when applicable: blinded) study drug. For SAEs and AESIs, a detailed narrative summarizing the course of the event, including its evaluation, treatment, and outcome should be provided on the AE eCRF. Specific or estimated dates of event onset, treatment, and resolution should be included, when available. Medical history, concomitant medications, and laboratory data that are relevant to the event should also be summarized in the narrative. For fatal events, the narrative should state whether an autopsy was or will be performed,

and include the results if available. Information not available at the time of the initial report must be documented in a follow-up report. Source documents (including hospital or medical records, diagnostic reports, etc.) will be summarized in the narrative on the AE eCRF, and retained at the study center and available upon request.

Urgent safety queries must be followed up and addressed promptly. Follow-up information and response to non-urgent safety queries should be combined for reporting to provide the most complete data possible within each follow-up.

10.1.3. Events that Require Expedited Reporting to Sponsor

The following events also require reporting to the Sponsor (or designee) within 24 hours of learning of the event:

SAEs.

Adverse Events of Special Interest (AESI):

- Grade ≥ 3 injection-site reactions
- Grade ≥ 3 hypersensitivity reactions

Note: refer to [Table 4](#) for grading scale.

- Multisystem inflammatory syndrome in children (MIS-C)

Note: MIS-C is defined according to the CDC ([CDC, 2021c](#)). All of the following criteria must be met to qualify:

- *An individual aged <21 years presenting with fever ($\geq 38.0^{\circ}\text{C}$ for ≥ 24 hours, or report of subjective fever lasting ≥ 24 hours)*
- *Laboratory evidence of inflammation, including, but not limited to, one or more of the following: an elevated C-reactive protein (CRP), erythrocyte sedimentation rate (ESR), fibrinogen, procalcitonin, d-dimer, ferritin, lactic acid dehydrogenase (LDH), or interleukin 6 (IL-6), elevated neutrophils, reduced lymphocytes and low albumin*
- *Evidence of clinically severe illness requiring hospitalization, with multisystem (≥ 2) organ involvement (cardiac, renal, respiratory, hematologic, gastrointestinal, dermatologic or neurological)*
- *No alternative plausible diagnoses*
- *Positive for current or recent SARS-CoV-2 infection by RT-PCR, serology, or antigen test; or COVID-19 exposure within the 4 weeks prior to the onset of symptoms*

Pregnancy: Although pregnancy is not considered an AE, it is the responsibility of the Investigator to report to the Sponsor (or designee), within 24 hours of identification, any pregnancy occurring in a study participants, during the study or within 8 months of the last dose of study drug. Any complication of pregnancy affecting a female subject, and/or fetus and/or newborn that meets the SAE criteria, must be reported as an SAE. Outcome for all pregnancies should be reported to the Sponsor.

A pregnancy report form will be completed for each subject who becomes pregnant or is pregnant at the time the parent or guardian signs consent.

10.2. Definitions

10.2.1. Adverse Event

An AE is any untoward medical occurrence in a subject administered a study drug which may or may not have a causal relationship with the study drug. Therefore, an AE is any unfavorable and unintended sign (including abnormal laboratory finding), symptom, or disease which is temporally associated with the use of a study drug, whether or not considered related to the study drug (ICH E2A Guideline. Clinical Safety Data Management: Definitions and Standards for Expedited Reporting, Oct 1994).

10.2.2. Serious Adverse Event

An SAE is any untoward medical occurrence that at any dose:

- Results in **death** – includes all deaths, even those that appear to be completely unrelated to study drug (eg, a car accident in which a subject is a passenger).
- Is **life-threatening** – in the view of the Investigator, the subject is at immediate risk of death at the time of the event. This does not include an AE that, had it occurred in a more severe form, might have caused death.
- Requires in-patient **hospitalization** or **prolongation of existing hospitalization**. In-patient hospitalization is defined as a hospital admission (any duration) or an emergency room visit for longer than 24 hours. Prolongation of existing hospitalization is defined as a hospital stay that is longer than was originally anticipated for the event, or is prolonged due to the development of a new AE as determined by the Investigator or treating physician.
- Results in persistent or significant **disability/incapacity** (substantial disruption of one's ability to conduct normal life functions).
- Is a **congenital anomaly/birth defect**
- Is an **important medical event** - Important medical events may not be immediately life-threatening or result in death or hospitalization, but may jeopardize the subject or may require intervention to prevent one of the other serious outcomes listed above (eg, intensive treatment in an emergency room or at home for allergic bronchospasm; blood dyscrasias or convulsions that do not result in hospitalization; or development of drug dependency or drug abuse).

Criteria for reporting SAEs must be followed for these events.

10.2.3. Adverse Events of Special Interest

An adverse event of special interest (AESI; serious or non-serious) is one of scientific and medical interest specific to the Sponsor's product or program, for which ongoing monitoring and rapid

communication by the Investigator to the Sponsor can be appropriate. Such an event might warrant further investigation in order to characterize and understand it.

10.2.4. Severity

The severity of AEs (including test findings classified as AEs) and injection-site-related reactions will be graded using the current version of the NCI-CTCAE v5.0 ([DCTD, 2017](#)). The NCI-CTCAE severity grading systems for anaphylaxis, allergic reaction, and injection site reaction are specifically provided in [Table 4](#).

Table 4: NCI-CTCAE Severity Grading (v5.0) for Anaphylaxis, Allergic Reaction, and Injection Site Reactions

CTCAE Term	Grade 1	Grade 2	Grade 3	Grade 4	Grade 5
				Only grade 3, 4, and 5 are reportable as AESI ¹	
Anaphylaxis ²	Not applicable	Not applicable	Symptomatic bronchospasm, with or without urticaria; parenteral intervention indicated; allergy-related edema/angioedema; hypotension	Life-threatening consequences; urgent intervention indicated	Death
Allergic reaction (hypersensitivity reaction) ³	Systemic intervention not indicated	Oral intervention indicated	Bronchospasm; hospitalization indicated for clinical sequelae; intravenous intervention indicated	Life-threatening consequences; urgent intervention indicated	Death
Injection site reaction ⁴	Tenderness with or without associated symptoms (eg, warmth, erythema, itching)	Pain; lipodystrophy; edema; phlebitis	Ulceration or necrosis; severe tissue damage; operative intervention indicated	Life-threatening consequences; urgent intervention indicated	Death

¹ See details in Section 10.1.3.

² Definition: A disorder characterized by an acute inflammatory reaction resulting from the release of histamine and histamine-like substances from mast cells, causing a hypersensitivity immune response. Clinically, it presents with breathing difficulty, dizziness, hypotension, cyanosis and loss of consciousness and may lead to death

³ Definition: A disorder characterized by an adverse local or general response from exposure to an allergen.

⁴ Definition: A disorder characterized by an intense adverse reaction (usually immunologic) developing at the site of an injection.

Source: (DCTD, 2017)

10.2.5. Causality

The Investigator must provide causality assessment as whether or not there is a reasonable possibility that the drug caused the adverse event, based on evidence or facts, his/her clinical judgment, and the following definitions. The causality assessment must be made based on the available information and can be updated as new information becomes available.

The following factors should be considered when assessing causality:

- Temporal relationship: time to onset versus time drug was administered
- Nature of the reactions: immediate versus long term
- Clinical and pathological features of the events
- Existing information about the drug & same class of drugs
- Concomitant medications
- Underlying and concurrent illnesses
- Response to dechallenge (drug discontinuation)
- Response to rechallenge (re-introduction of the drug)
- Patient's medical and social history

Causality to the study drug (including study drug administration):

- Related:
 - The AE follows a reasonable temporal sequence from study drug administration, and cannot be reasonably explained by the nature of the reaction, patient's clinical (eg, disease under study, concurrent diseases, concomitant medications), or other external factors.

or

- The AE follows a reasonable temporal sequence from study drug administration, and is a known reaction to the drug under study or its class of drugs, or is predicted by known pharmacology.

- Not Related:
 - The AE does not follow a reasonable sequence from study drug administration, or can be reasonably explained by the nature of the reaction, patient's clinical state (eg, disease under study, concurrent diseases, and concomitant medications) or other external factors.

Causality to the study conduct (protocol specified procedure):

- Related:
 - The AE follows a reasonable temporal sequence from a protocol specified procedure, and cannot be reasonably explained by the nature of the reaction, patient's clinical (eg, disease under study, concurrent diseases, concomitant medications), or other external factors.
- Not Related:
 - The AE does not follow a reasonable sequence from a protocol specified procedure, or can be reasonably explained by the nature of the reaction, patient's clinical state (eg, disease under study, concurrent diseases, and concomitant medications) or other external factors.

10.3. Safety Monitoring

The Investigator will monitor the safety of study subject at his/her site(s) as per the requirements of this protocol and consistent with current Good Clinical Practice (GCP). Any questions or concerns should be discussed with the Sponsor in a timely fashion. The Sponsor will monitor the safety data from across all study sites. The Medical/Study Director will have primary responsibility for the emerging safety profile of the compound, but will be supported by other departments (eg, Global Patient Safety; Biostatistics and Data Management). Safety monitoring will be performed on an ongoing basis (eg, individual review of SAEs) and on a periodic cumulative aggregate basis.

10.4. Notifying Health Authorities, Institutional Review Boards, and Investigators

During the study, the Sponsor and/or the contract research organization (CRO) will inform health authorities, IRBs, and the participating Investigators of any SUSARs (Suspected Unexpected Serious Adverse Reactions) occurring in other study centers or other studies of the active study drug, as appropriate per local reporting requirements. In addition, the Sponsor and/or CRO will comply with any additional local safety reporting requirements.

Upon receipt of the Sponsor's notification of a SUSAR that occurred with the study drug, the Investigator will inform the Institutional Review Board (IRB) unless delegated to the Sponsor.

Event expectedness for study drug is assessed against the Reference Safety Information section of the Investigator's Brochure that is effective for expedited safety reporting.

At the completion of the study, the Sponsor will report all safety observations made during the conduct of the trial in the Clinical Study Report to health authorities and IRB as appropriate.

11. STATISTICAL PLAN

This section provides the basis for the statistical analysis plan (SAP) for the study. The SAP will be revised prior to the end of the study to accommodate amendments to the clinical study protocol and to make changes to adapt to unexpected issues in study execution and data that may affect the planned analyses. The final SAP will be issued before the first database lock.

Endpoints are listed in Section 4. Analysis variables are listed in Section 5.

11.1. Statistical Hypothesis

No formal statistical hypothesis testing is planned in this study. The pharmacokinetics hypothesis for this study is defined in Section 3.2.3.1.

11.2. Justification of Sample Size

Analyses of PK, safety, tolerability, immunogenicity, and serology data will be descriptive. The sample size was chosen based on PK considerations and is consistent with early phase studies to assess PK.

At least 12 subjects are needed to enroll in each weight group (Group A: ≥ 10 kg to <40 kg, and Group B: ≥ 3 kg to <10 kg) to assess drug concentration. The study plans to enroll approximately 28 subjects in total.

The sample size may be adjusted if planned SC dosing of casirivimab+imdevimab does not achieve concentrations in serum similar to, or higher than, that observed in adults (≥ 18 years of age) after casirivimab+imdevimab 1200 mg (600 mg per mAb) SC administration. PK will be evaluated on an ongoing basis to determine if dose adjustments are needed and whether more subjects are needed for analysis.

11.3. Analysis Sets

11.3.1. Safety Analysis Set

The safety analysis set (SAF) includes all subjects who received any study drug; it is based on the treatment received (as treated). Treatment compliance/administration and all clinical safety variables will be analyzed using the SAF.

11.3.2. Pharmacokinetic Analysis Set

The PK analysis population includes all subjects who received any study drug and who had at least 1 non-missing result following the first dose of study drug. Subjects will be analyzed based on the actual treatment received.

11.3.3. Immunogenicity Analysis Sets

The ADA analysis sets (AAS) include all subjects who received any study drug and had at least one non-missing ADA result following the first dose of the study drug. The AAS is based on the actual treatment received (as treated).

The NAb analysis sets (NAS) includes all subjects who received any study drug, have at least one non-missing result following the first dose of study drug, and either tested negative at all ADA sampling times or tested positive for ADA with at least one non-missing NAb result after first dose of study drug. Subjects who are ADA negative are set to negative in the NAb analysis set.

11.4. Statistical Methods

For continuous variables, descriptive statistics will include the following information: the number of subjects reflected in the calculation (n), mean, standard deviation, Q1, median, Q3, minimum, and maximum.

For categorical or ordinal data, frequencies and percentages will be displayed for each category.

11.4.1. Subject Disposition

The following will be provided:

- The total number of screened subjects whose parent(s) or guardian signed the ICF
- The total number of subjects who discontinued the study, and the reasons for discontinuation

11.4.2. Demography and Baseline Characteristics

Demographic and baseline characteristics will be summarized descriptively by weight group and by all subjects combined.

11.4.3. Safety Analysis

11.4.3.1. Adverse Events

Definitions

For safety variables, 2 observation periods are defined:

- The pretreatment period is defined as the time from the parent(s)/guardian(s) signing the ICF to before study drug administration.
- The on-treatment period is defined as the time of study drug administration to the last study visit.

Treatment-emergent adverse events are defined as those that are not present at baseline or represent the exacerbation of a pre-existing condition during the on-treatment period.

Analysis

All AEs reported in this study will be coded using the Medical Dictionary for Regulatory Activities (MedDRA®).

Summaries of all TEAEs by treatment group will include:

- The number (n) and percentage (%) of subjects with at least 1 TEAE by SOC and PT
- TEAEs by severity (according to the grading scale outlined in Section 10.2.4), presented by SOC and PT

- Treatment-related TEAEs presented by SOC and PT
- Treatment-emergent AESIs (defined with a PT or a prespecified grouping)

Treatment-emergent adverse events leading to permanent treatment discontinuation will be summarized by weight group.

11.4.3.2. Other Safety

Vital Signs

Vital signs (temperature, pulse, blood pressure, and respiration rate) will be summarized by baseline and change from baseline to each scheduled assessment time with descriptive statistics.

Laboratory Tests

Laboratory test results will be summarized by baseline and change from baseline to each scheduled assessment time with descriptive statistics.

Number and percentage of subjects with a potentially clinically significant value (PCSV) at any post-study drug administration time point will be summarized for each clinical laboratory test for all subjects and separately for subjects in whom the PCSV criterion was normal or missing at baseline.

Shift tables based on baseline normal/abnormal and other tabular and graphical methods may be used to present the results for laboratory tests of interest.

11.4.3.3. Treatment Exposure

The duration of study treatment exposure will be defined as 28 days after the last dose for a subject in SAF.

11.4.3.4. Treatment Compliance

Subject treatment compliance is not applicable for this study, since the study drug is administered once at the site and will be the same as treatment exposure.

11.4.4. Pharmacokinetics

11.4.4.1. Analysis of Drug Concentration Data

Analysis will be performed according to two groups:

- Group A: body weight ≥ 10 kg to < 40 kg
- Group B: body weight ≥ 3 kg to < 10 kg

The concentrations of total casirivimab and total imdevimab over time will be summarized by descriptive statistics for each weight group.

Subjects who test positive for SARS-CoV-2 infection during the treatment period may be analyzed separately from the PK analysis population.

Stratification of the analysis may be performed if subjects receive a treatment that has the potential to impact the pharmacokinetics of casirivimab+imdevimab (eg, IVIG)

No formal statistical hypothesis testing will be performed.

11.4.5. Analysis of Immunogenicity Data

11.4.5.1. Analysis of ADA Data

The immunogenicity variables described in Section 5.4 will be summarized using descriptive statistics. Immunogenicity will be characterized by ADA status, ADA category, and maximum titer observed in patients in the ADA analysis sets.

The ADA status of each patient may be classified as one of the following:

- Positive
- Pre-existing – If the baseline sample is positive and all post baseline ADA titers are reported as less than 9-fold the baseline titer value
- Negative – If all samples are found to be negative in the ADA assay.

The ADA category of each positive patient is classified as one of the following:

- Treatment-boosted - A positive result at baseline in the ADA assay with at least one post baseline titer result \geq 9-fold the baseline titer value
- Treatment-emergent - A negative result or missing result at baseline with at least one positive post baseline result in the ADA assay. Patients that are treatment-emergent may be further categorized.

The maximum titer category of each patient is classified as:

- Low (titer $<1,000$)
- Moderate ($1,000 \leq$ titer $\leq 10,000$)
- High (titer $>10,000$)

Listings of all ADA titer levels will be provided for patients with pre-existing, treatment-emergent and treatment-boosted ADA response.

Plots of drug concentrations will be examined and the influence of ADAs on individual PK profiles evaluated. Assessment of impact of ADA on safety and efficacy may be provided.

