Length of Follow-up Period. Subjects will undergo a follow-up period of approximately 24 weeks (six months) for assessment of drug concentrations, safety, and immunogenicity. In COV-2069, a single 1200 mg SC dose resulted in an observed half-life of approximately 32.4 days (casirivimab) and 27.0 days (imdevimab). The duration of the follow-up period in the current study is thus intended to allow observation of drug concentration and safety in subjects for more than five half-lives (six months) following study drug administration. The length of the follow-up period may be modified based on drug concentration data observed in this study, as well as ongoing nonclinical data as they become available.

Collection of Serology for SARS-CoV-2 Serostatus. Subjects will be assessed for antibodies against SARS-CoV-2, which may include but not be limited to antibodies against spike (S) and/or nucleocapsid (N) protein, at the screening/baseline visit and (depending on the subject's weight at the time of study drug administration) during scheduled and/or unscheduled visits following study drug administration. These assessments will allow detection of prior SARS-CoV-2 infection and/or seroconversion subsequent to a SARS-CoV-2 infection that occurs during the study.

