	≥2.5 to <5 kg	50 mg SC	59.9 (41.0, 90.1)	52.5 (36.9, 77.5)
	<2.5 kg	25 mg SC	49.0 (35.9, 71.4)	42.9 (32.3, 61.2)
C _{max} (mg/L)	Adult	600 mg SC	51.1 (33.4, 72.6)	48.2 (32.2, 67.8)
	≥40 kg	600 mg SC	55.8 (32.4, 97.6)	52.6 (31.2, 91.1)
	≥20 to <40 kg	400 mg SC	92.1 (58.2, 139.4)	86.5 (55.6, 129.4)
	≥10 to <20 kg	200 mg SC	85.0 (54.6, 131.5)	79.7 (52.1, 121.5)
	≥5 to <10 kg	75 mg SC	69.3 (42.9, 104.0)	64.6 (40.8, 95.1)
	≥2.5 to <5 kg	50 mg SC	83.8 (54.4, 127.7)	77.2 (51.5, 115.6)
	<2.5 kg	25 mg SC	71.2 (49.7, 107.0)	65.0 (46.9, 96.3)
AUC ₀₋₂₈ (mg*day/L)	Adult	600 mg SC	1093 (752, 1533)	993 (708, 1361)
	≥40 kg	600 mg SC	1214 (738, 2087)	1104 (693, 1868)
	≥20 to <40 kg	400 mg SC	2060 (1331, 3052)	1865 (1238, 2714)
	≥10 to <20 kg	200 mg SC	1956 (1274, 3048)	1775 (1180, 2746)
	≥5 to <10 kg	75 mg SC	1648 (1031, 2452)	1508 (961, 2197)
	≥2.5 to <5 kg	50 mg SC	1976 (1298, 2980)	1796 (1216, 2661)
	<2.5 kg	25 mg SC	1657 (1182, 2474)	1497 (1107, 2200)

¹All values are represented as median (5th percentile, 95th percentile).

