7. Urine pregnancy test will be performed for all women of childbearing potential (WOCBP), regardless of pregnancy status. If urine pregnancy test is positive, a serum pregnancy test will be performed for confirmation. A pregnancy report form will be completed for each subject who becomes pregnant or is pregnant at the time the parent or guardian signs consent.
8. Study drug will be administered after all sample collections and assessments are completed for the study visit.
9. Vital signs will be recorded prior to study drug administration, and approximately 1 hour after study drug administration. Vital signs may additionally be recorded as needed per local standard of care and Investigator discretion.

10. In the event that limited availability of blood prevents the collection of all indicated blood samples for a given visit, PK-ADA sample collection (when applicable) will be prioritized over other blood samples.
11. The indicated blood samples may be collected at either the screening or pre-dose visit, but must be collected prior to study drug administration. Efforts should be made to collect all screening/pre-dose blood samples on the same day, when feasible.
12. Indicated hematology/blood chemistry sample collection is optional, and may be collected if considered clinically appropriate by the investigator or designee.
13. On day 1, subjects in group A and group B will each be assigned using IWRS to one of two staggered PK-ADA sampling schedules (schedule 1 and schedule 2).
14. Actual dosing time and sample collection times will be recorded for all drug concentration/immunogenicity (“PK-ADA”) samples. The pre-dose PK-ADA sample collection must be performed on the same day as study drug administration. The window for pre-dose PK-ADA sample collection is as close to administration of study drug as is reasonable.
15. PK-ADA sample may be analyzed for ADA and NAb, if feasible, in samples collected pre-dose, on day 29 (schedule 1), and on day 85 (schedule 2).

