9.2.8. Exploratory Biomarkers

9.2.8.1. Serological Assays for Endogenous Anti-SARS-CoV-2 Antibody Responses

Antibodies against SARS-CoV-2 will be measured at baseline in all subjects. Antibodies may include, but may not be limited to, anti-S IgA and IgG and anti-N IgG antibodies measured using immunoassays. Anti-SARS-CoV-2 antibodies will be measured at timepoints post-baseline, as specified in the schedule of events, in order to explore the underlying prevalence of SARS-CoV-2 antibody positivity, and seroconversion (compared to baseline) in the study population with casirivimab+imdevimab. The assays used post-baseline to measure antibody immunity will have been demonstrated to not be susceptible to interference from casirivimab+imdevimab and may include but may not be limited to anti-N IgG immunoassays. Neutralization assays that detect anti-SARS-CoV-2 neutralizing antibodies may also be used to explore whether a positive anti-SARS-CoV-2 antibody response was comprised of functionally neutralizing antibodies.

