5.10. Analysis of Immunogenicity Data

5.10.1. Analysis of ADA Data

The immunogenicity variables described in Section [4.8](#) will be summarized using descriptive statistics. Immunogenicity will be characterized per drug molecule by ADA status, ADA category and maximum titer observed in participants in the ADA analysis sets. For samples confirmed as drug specific ADA positive, but found negative at the lowest titer dilution, the lowest dilution in the titer assay is imputed.

The ADA status of each participant may be classified as one of the following:

Positive

Pre-existing - If the baseline sample is positive and all post baseline ADA titers are reported as less than 9-fold the baseline titer value

Negative - If all samples are found to be negative in the ADA assay.

The ADA category of each positive participant is classified as:

Treatment-boosted - A positive result at baseline in the ADA assay with at least one post baseline titer result \geq 9-fold the baseline titer value

Treatment-emergent - A negative result or missing result at baseline with at least one positive post baseline result in the ADA assay.

The maximum titer category of each participant is classified as:

Low (titer $<1,000$)

Moderate ($1,000 \leq$ titer $\leq 10,000$)

High (titer $>10,000$)

The following will be summarized by treatment group and ADA titer level:

- Number (n) and percent (%) of ADA-negative participants
- Number (n) and percent (%) of pre-existing participants
- Number (n) and percent (%) of treatment-emergent ADA positive participants
 - Number (n) and percent (%) of persistent treatment-emergent ADA positive participants
 - Number (n) and percent (%) of indeterminate treatment-emergent ADA positive participants
 - Number (n) and percent (%) of transient treatment-emergent ADA positive participants
- Number (n) and percent (%) of treatment-boosted ADA positive participants

Listing of all ADA titer levels will be provided for participants with pre-existing, treatment-emergent and treatment-boosted ADA response.

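### Every assay-negative child is counted as ADA-negative whatever the drug level in the sample, and the plan has no drug-tolerance check to show which negatives can be relied on

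*Protocol*

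**What the plan says.** **Status rule.** Protocol 11.4.5.1 offers three statuses: Positive, Pre-existing and Negative. A participant is Negative "If all samples are found to be negative in the ADA assay". SAP 5.10.1 repeats this: "Negative - If all samples are found to be negative in the ADA assay". A participant positive at baseline is Pre-existing unless a post-dose titre reaches 9 times the baseline titre. Neither document states a drug tolerance for the ADA assays, compares an ADA result with the drug level in the same sample, or provides an inconclusive class for negatives. The SAP's indeterminate class is a subset of treatment-emergent positives.

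**Sampling.** Footnote 15 to the Schedule of Events (protocol 9.1.1) says that PK-ADA samples may be "analyzed for ADA and NAb, if feasible, in samples collected pre-dose, on day 29 (schedule 1), and on day 85 (schedule 2"). Footnote 13 says that children in each weight group are "assigned using IWRS to one of two staggered PK-ADA sampling schedules (schedule 1 and schedule 2"). Each child therefore has one named post-dose ADA time, apart from any early-termination or unscheduled PK-ADA draw.

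**Drug levels.** Protocol Table 1 (section 3.2.3.2) predicts C28 for each weight tier. The highest casirivimab entry among the tiers used here is "59.9 (41.0, 90.1"), as median with 5th and 95th percentiles in mg/L. Section 3.2.1 states that in COV-2069 "a single 1200 mg SC dose resulted in an observed half-life of approximately 32.4 days (casirivimab) and 27.0 days (imdevimab").

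**What else is planned.** Protocol 11.4.5.1 has concentration plots examined for the influence of ADA on PK; SAP 5.11.1 makes such plots optional. SAP 1.2.3 and 3.3 drop the NAb analysis, so ADA is the only immunogenicity measure left.

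**The concern.** An ADA assay can fail to detect antibody when enough drug is present in the sample. How much is enough is the assay's drug tolerance. A negative below that limit is evidence of no detectable ADA; a negative above it says little. The plan counts both the same way.

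Any error from this source runs in one direction. A masked positive moves into Negative. A post-dose titre suppressed by drug can miss the 9-fold test, so a boosted child is labelled Pre-existing. Nothing in the mechanism raises the ADA rate.

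Immunogenicity is a secondary endpoint (protocol 4.2) and its clinical consequences are an important potential risk (3.3.2). With about 28 children planned, a low or zero rate is likely to be read as reassurance. How much reassurance it gives depends on how many negatives could have been positive.

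**Working it through.** **1. The plan's own figure.** Section 3.2.1 says that follow-up exceeds five half-lives. From dosing on day 1 to day 169 is 168 days: 168/32.4 = 5.2 (casirivimab) and 168/27.0 = 6.2 (imdevimab). The statement reproduces.

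**2. Day 29.** Study day 29 is 28 days after dosing, so Table 1's C28 applies. Medians (5th, 95th percentile), mg/L:

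| Tier in Table 1 | Casirivimab | Imdevimab |
|---|---|---|
| ≥20 to <40 kg | 56.9 (37.0, 85.9) | 48.6 (32.2, 72.3) |
| ≥10 to <20 kg | 57.1 (36.3, 91.8) | 49.3 (31.8, 79.3) |
| ≥5 to <10 kg | 51.0 (32.2, 75.3) | 45.1 (28.9, 64.8) |
| ≥2.5 to <5 kg | 59.9 (41.0, 90.1) | 52.5 (36.9, 77.5) |

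The study enrols from 3 kg, so the last row is the nearest available tier.

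**3. Day 85.** The gap is 56 days. With first-order decline, ratio = 2^(56/half-life).
- Casirivimab: 2^(56/32.4) = 3.3, giving medians of 15.4 to 18.1 mg/L.
- Imdevimab: 2^(56/27.0) = 4.2, giving medians of 10.7 to 12.5 mg/L.
- With the ±3-day windows (gap 50 to 62 days), the ratios are 2.9 to 3.8 and 3.6 to 4.9.

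**4. Sensitivity to the half-life.** The half-lives are adult values. A rough paediatric decline can be read from Table 1 medians as k = ln(Cmax/C28)/(28 − Tmax). Tmax is not given, so it is assumed. Example, casirivimab, ≥5 to <10 kg, Tmax 7 days: k = ln(69.3/51.0)/21 = 0.0146 per day, half-life 47.5 days, ratio 2.3, day-85 median 22.5 mg/L. Ratios across the four tiers:

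| Assumed Tmax | Casirivimab | Imdevimab |
|---|---|---|
| 4 days | 2.1 to 3.1 | 2.3 to 3.8 |
| 7 days | 2.3 to 3.6 | 2.6 to 4.7 |
| 10 days | 2.6 to 4.5 | 3.1 to 6.0 |

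**5. What tolerance would do.** The documents give none, so these are assumptions.
- 30 mg/L: every day-29 median is above it, and so is every 5th percentile except imdevimab at ≥5 to <10 kg (28.9). Every day-85 median is below it.
- 100 mg/L: even the highest day-29 95th percentile (91.8) is below it.

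**6. Effect on the reported rate.** Assume 14 children per schedule (the allocation ratio is not stated), true rate p, and a fraction m of schedule 1 positives masked. Observed rate = [14p(1 − m) + 14p]/28.
- p = 20%, m = 0.5: (1.4 + 2.8)/28 = 15%.
- p = 20%, m = 1: 2.8/28 = 10%.
- p = 10%, m = 1: 1.4/28 = 5%.

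For zero positives, the exact two-sided 95% upper limit is 1 − 0.025^(1/n): 12.3% for n = 28 and 23.2% for n = 14.

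**7. Choosing the denominator.** Take p = 20%, m = 0.5, all day-29 samples above tolerance and all day-85 samples below.
- Dropping only the high-drug negatives leaves 2.8 + 1.4 = 4.2 positives among 14 + 1.4 = 15.4 children, or 27%. With no masking at all it gives 5.6/16.8 = 33%. Both overshoot 20%, because high-drug positives stay in.
- Restricting by concentration whatever the ADA result gives 2.8/14 = 20%.

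**The case against.** **No harm is demonstrated.** Nothing in either document says that these assays are affected by drug at these levels. The tolerance may be recorded in assay documents outside the protocol and SAP. The 30 mg/L limit, the 20% incidence and the masking fractions above are all assumed. This objection stands, and it keeps the point conditional.

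**Schedules differ in more than drug level.** A reader might infer that a lower ADA rate on schedule 1 would reveal masking. It would not: day 29 also allows less time for ADA to develop than day 85. Only the concentration in each sample can separate the two explanations.

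**The serology section is not a precedent.** Section 9.2.8.1 requires that "The assays used post-baseline to measure antibody immunity will have been demonstrated to not be susceptible to interference from casirivimab+imdevimab". A reader might take this as showing that an equivalent ADA condition was overlooked. The comparison is weak. Those assays look for the child's own anti-SARS-CoV-2 antibodies, and the study drugs bind the spike protein, so the obvious risk there is a false positive. ADA masking is a false negative in a different assay.

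**Mitigation and stakes.** Concentration plots could reveal ADA that lowers exposure, and titres of Pre-existing participants are listed. Extra PK-ADA draws may give some children a second result, and the SAP's persistent and transient subclasses suggest that more than one was expected. The analysis is descriptive and small: 20% against 15% of 28 is 1.4 children. All of this limits the consequence. None of it changes a child's ADA status or tells the reader how many negatives are verifiable.

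**Conclusion.** The gap is real, but its effect is conditional. The plan calls a child Negative on the assay result alone, at predicted median drug levels of 45 to 60 mg/L (schedule 1) or about 11 to 18 mg/L (schedule 2), and supplies nothing by which those negatives can be checked.

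A reader might conclude that the plan does understate immunogenicity. The documents do not support that. If tolerance is well above 100 mg/L, the effect at the named times is nil. If it is about 30 mg/L, most schedule 1 negatives cannot be verified, and any resulting error can only lower the rate, at most halving it if masking is confined to schedule 1 and the schedules are equal in size.

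This rests on model-predicted C28, adult half-lives carried to day 85, and an assumed equal split. Enrolment was paused on 28 December 2021 (SAP section 1), so the final numbers may be below 28; the upper limits for zero positives would then be wider.

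**What to change.** In SAP 5.10.1:

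1. Keep the planned ADA status table as it is.
2. State the validated drug tolerance of each ADA assay.
3. Flag every post-dose ADA result that is negative, or positive but under the 9-fold rule, when the paired concentration of that antibody exceeds the tolerance. Including the second kind covers a boosted child labelled Pre-existing.
4. Report, per antibody and by schedule, the number of Negative and of Pre-existing participants with no post-dose sample at or below tolerance.
5. Add a supportive ADA rate restricted to participants with a post-dose sample at or below tolerance, regardless of ADA result, so that numerator and denominator are selected in the same way.

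The supportive rate should not replace the main table. If ADA speeds drug clearance, positive children are more likely to fall below tolerance, so some selection remains.

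The cost is one derived flag and one extra table. Concentration and ADA come from the same PK-ADA draw, so no extra blood is needed. Some negatives will be shown as inconclusive, and with a low tolerance this could be most of schedule 1. With a high tolerance no child is flagged, and the planned table stands with its negatives verified.
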